3.2. METHOD OF ASSIGNING SUBJECTS TO TREATMENT GROUPS

Randomization will be stratified by region. The treatment schedule will be generated by a non-study biostatistician. Once a subject is deemed eligible to be randomized at Day -1, an interactive voice/web-based system (IXRS) will perform the treatment assignment. Subjects will be randomized to 1 of 3 treatments in a 1:1:1 ratio:

- SEP-4199 200 mg/day
- SEP-4199 400 mg/day
- Placebo QD

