3.4. DETERMINATION OF SAMPLE SIZE

A total sample size of 279 evaluable subjects in US and Europe (93 per treatment group: SEP-4199 200 mg/day, SEP-4199 400 mg/day, and placebo) with a global 2-sided alpha of 0.05 will provide about 90% power to reject at least 1 truly significant primary comparison and about 75% power to reject both truly significant primary comparisons using the truncated Hochberg ($\gamma = 0.9$) procedure, assuming treatment effect sizes of 0.44 for both doses of SEP-4199. The effect sizes were selected considering the data from the completed Lurasidone bipolar depression monotherapy study (Loebel 2014). This effect size corresponds to a treatment difference of -3.85 for a SEP-4199 dose with a common standard deviation of 8.745 on the MADRS scale change from baseline at Week 6. An upward adjustment of approximately 5% is used to compensate for information lost due to subjects who are randomized and do not provide any postbaseline primary efficacy data. The total sample size will be approximately 294 randomized subjects (or $N = 98$ subjects per treatment group).

For the secondary efficacy endpoint, assuming the 93 subjects per treatment arm, the study will have 71% power to reject at least one truly significant comparison within the CGI-BP-S family using the regular Hochberg procedure, given a treatment difference of -0.47 for a SEP-4199 dose with a common standard deviation of 1.24 on the CGI-BP-S change from baseline at Week 6. The correlation between the primary and the secondary endpoint is assumed to be 0.8 for each treatment arm.

The sample size was calculated using the Mediana package version 1.05 within R version 3.4.2 ([R Core Team 2017](#))

See [APPENDIX 4](#) for additional power and Type I error rate calculations.

The sample size for the Japanese cohort (45 total [$N = 15$ subjects per group], including 9 dropouts) provides more than 80% probability to have a treatment difference point estimate greater than zero for the MADRS.

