robustness of the conclusions, as indicated in [Section 16.2.4](#).

D. Population level summary of the variable: Difference in means of change from baseline in MADRS total score at Week 6 comparing each SEP-4199 treatment group to placebo

The efficacy of SEP-4199 in terms of the MADRS total score will be evaluated using the following two null hypotheses:

H1: There is no difference in mean change from baseline at Week 6 on the MADRS total score in the SEP-4199 200 mg treatment arm compared to Placebo.

H2: There is no difference in mean change from baseline at Week 6 on the MADRS total score in the SEP-4199 400 mg treatment arm compared to Placebo.

The alternative hypothesis for each of the null hypotheses is that there is a difference. If at least 1 of the primary treatment group comparisons demonstrate a significant result, the study will be considered positive.

The primary efficacy endpoint will be analyzed for the ITT population using an MMRM analysis, with change from baseline in the MADRS total score as the response variable and with factors for treatment group, week, region, baseline MADRS total score, and the treatment-by-week interaction. This analysis method makes an MAR assumption to the missing primary efficacy endpoints. The Kenward Roger approximation will be used to estimate denominator degrees of freedom. An unstructured covariance matrix will be used for the within-subject correlation. A robust sandwich estimator for the standard error of the fixed effects ([Diggle 2002](#)) along with a spatial exponential or a spatial power covariance structures will be assumed sequentially in case the model fails to convergence. The first covariance structure to yield convergence will be used in the analysis.

The Least Square (LS) mean treatment differences (each SEP-4199 group minus placebo) of change from baseline at Week 6, their 2-sided 95% CIs, and the associated p-values will be calculated based on the MMRM. The LS mean of change from baseline over time will be plotted. Adjusted p-values will be calculated using a truncated Hochberg procedure with gamma parameter=0.9 (See [Section 7.4](#)).

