The remaining monotone missing data will be imputed using sequential regression multiple imputation, where a separate regression model is estimated for imputation of each variable (ie, MADRS total score at each time point). Imputation of values in the placebo group will assume MAR. Imputation of values in the SEP-4199 (200 or 400 mg/day) group will be done as if the subject had been a member of the placebo group. Missing values in the SEP-4199 (200 or 400 mg/day) groups will be imputed using the imputation model of the placebo group, ie, conditional on subject values observed at time points prior to discontinuation. Each sequential regression model (ie, for imputation of values at a given time point) will include explanatory variables for all previous (Baseline, Week 1, Week 2, and Week 4) values of MADRS total score. Missing values at a given time point in placebo and SEP-4199 (200 or 400 mg/day) treatment groups will be imputed from the same imputation model, conditional on subject values observed or imputed at previous time points. The SAS MI procedure with the MONOTONE REG statement is used to specify that the regression method will be used for the imputation, and the MNAR statement with MODEL option will be used for the MADRS total score at each postbaseline visit to specify that only observations from the placebo group should be used to estimate the imputation model. The random seed number is 56789.

No rounding restriction will be applied to imputed MADRS total scores. The imputed MADRS total scores must be within the range of 0 to 60.

Each of the 1000 imputed datasets will be analyzed using the same MMRM model as the primary efficacy analysis. Results from the analysis of each imputed dataset, ie, the LS means of each treatment group, the LS mean treatment difference, and their standard errors, will be combined using Rubin's imputation rules (using the SAS MIANALYZE procedure) to produce pooled LS mean estimates, their standard errors and 95% CI, and a pooled p-value for the test of null hypothesis of no treatment effect.

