APPENDIX 3. STATISTICAL MODEL SPECIFICATIONS

MIXED MODEL FOR REPEATED MEASURES (MMRM)

Ods graphics on;

```
PROC MIXED DATA=XXX plots=(studentpanel(marginal) pearsonpanel(marginal));
```

```
  CLASS SUBJID REGION TRTPN WEEK;  
  MODEL TOTCFB = TOTBL REGION TRTPN WEEK TRTPN*WEEK / DDFM=KR RESIDUAL OUTPM=OUTRESIDUAL;  
  REPEATED WEEK/TYPE=UN SUBJECT=SUBJID;  
  LSMEANS TRTPN*WEEK /PDIFF CL;
```

RUN;

*Where WEEK = Week 1, Week 2, Week 4, Week 6;

Ods graphics off;

In case the MMRM model assuming the unstructured covariance variance structure fails to converge, the spatial exponential or spatial power covariance structure will be assumed sequentially along with a robust sandwich estimator. The first covariance structure to yield convergence will be used in the analysis.

```
PROC MIXED EMPIRICAL;
```

```
  CLASS SUBJID REGION TRTPN WEEK;  
  MODEL TOTCFB = TOTBL REGION TRTPN WEEK TRTPN*WEEK / RESIDUAL OUTP=OUTRESIDUAL;  
  REPEATED WEEK/TYPE=SP(EXP) (WEEK) SUBJECT=SUBJID;  
  REPEATED WEEK/TYPE=SP(POW) (WEEK) SUBJECT=SUBJID;  
  LSMEANS TRTPN*WEEK /PDIFF CL COV;
```

RUN;

*EMPIRICAL IS FOR THE SANDWICH ESTIMATOR;

Within-group effect size will be calculated as the absolute value of LS mean of change from baseline divided by SD, obtained as the SE of the LS Mean multiplied by the square root of the treatment group change from baseline sample size at each visit. Between-group effect size at a visit will be calculated as the absolute value of the LS means difference from Placebo divided by the model estimate of the pooled SD at the visit, which is obtained from the square root of the diagonal element, associated at the visit, from the covariance matrix (R matrix of subjects with MADRS total score at all visits). Although the variance-covariance estimates are calculated differently depending on the covariance structure being applied for the model, the diagonal of the R matrix will contain the variance estimate at each visit that can be used for the effect size calculations regardless of the covariance structure.

Document:

Author:

Version Number:

V2.0

Version Date:

21MAY2020

Template No: CS_TP_BS016 Revision 4
Effective Date: 01Apr2016

Reference: CS_WI_BS005

For All SEP-4199 column for safety questionnaires:

- LS Means estimate, 95%CI and SE is obtained using following statements:

```
LSMESTIMATE TRT01PN*AVISITN "MEAN(200MG+400MG) at Week 1" [1, 1 1] [1, 2 1] / CL divisor=2;  

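### The primary MMRM holds the baseline MADRS slope constant over all four post-baseline weeks; a baseline-by-week term costs 3 parameters and may modestly improve Week 6 precision

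*SAP*

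**What the plan says.** The response in the primary analysis is change from baseline in MADRS total score. SAP 16.1.3 models it "with factors for treatment group, week, region, baseline MADRS total score, and the treatment-by-week interaction". The code in SAP Appendix 3 matches: "MODEL TOTCFB = TOTBL REGION TRTPN WEEK TRTPN*WEEK / DDFM=KR RESIDUAL OUTPM=OUTRESIDUAL". The baseline score, TOTBL, appears once and is not crossed with WEEK. The code comment lists the repeated time points: "Where WEEK = Week 1, Week 2, Week 4, Week 6". Protocol 15.3.5.1 gives the same terms, with visit in place of week.

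On the covariance, SAP 16.1.3 states: "An unstructured covariance matrix will be used for the within-subject correlation". That frees the residual variances and correlations. It does not free the mean model, where the baseline effect is still the same at every week.

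The supportive ANCOVA (SAP 16.1.5.1; run BY WEEK in Appendix 3) is fitted separately at each visit and so has its own Week 6 baseline slope. SAP 16.2.5 repeats it for CGI-BP-S.

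**The concern.** H1 and H2 are tested at Week 6 only. If the relation between baseline severity and change differs between Week 1 and Week 6, a single slope is a compromise. Generalised least squares gives more weight to the less variable early visits, so the compromise tends to sit near the Week 1 slope. Baseline is then under-adjusted at the visit that decides the trial, and the unexplained part goes into the Week 6 residual variance. What is at stake is the width of the Week 6 confidence interval and some power.

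**Working it through.** **1. The plan's own power.** Inputs from SAP 3.4 and Appendix 4: 93 evaluable subjects per arm, difference 3.85, SD 8.745, truncated Hochberg with gamma 0.9, one-sided 0.025.

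- Effect size: 3.85 / 8.745 = 0.440.
- Mean of each test statistic: 0.44 × √(93/2) = 3.00. The correlation is 0.5, from the shared placebo arm under 1:1:1 allocation.
- Rule: reject both if the larger p ≤ 0.95 × 0.025; otherwise reject the smaller if p ≤ 0.025/2.
- Result: 90.5% for at least one and 75.2% for both. Table 8 gives 0.9027 and 0.7517, so the stated power reproduces. It assumes nothing about visit-specific slopes.

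**2. Cost of the term.** Four slopes instead of one: 4 − 1 = 3 parameters, against 279 evaluable subjects.

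**3. What the common slope adds at Week 6.**

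Week 6 variance with a common slope = V6 + (b6 − bc)² × SDb²

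Here V6 is the residual variance when Week 6 has its own slope b6, bc is the fitted common slope, and SDb is the baseline SD. Only one input is in the documents: 8.745² = 76.5, used for V6. Assumed: SDs of 5, 6.5 and 8 at Weeks 1, 2 and 4; AR(1) correlation 0.75 between successive visits; SDb of 4 or 5; slopes as listed, changing in equal steps over the visits. The common slope comes from iterated population-level GLS with complete data.

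| Slope, Week 1 to Week 6 | Common slope | Gap at Week 6 | Added variance (SDb 4; 5) | Common-slope variance higher by | Adding the term lowers it by |
|---|---|---|---|---|---|
| equal | same | 0 | 0; 0 | 0%; 0% | 0%; 0% |
| -0.10 to -0.25 | -0.11 | -0.14 | 0.31; 0.49 | 0.4%; 0.6% | 0.4%; 0.6% |
| -0.15 to -0.45 | -0.18 | -0.27 | 1.17; 1.82 | 1.5%; 2.4% | 1.5%; 2.3% |
| -0.10 to -0.65 | -0.15 | -0.50 | 4.00; 6.25 | 5.2%; 8.2% | 5.0%; 7.6% |

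Example, last row with SDb 5: 0.50² × 25 = 6.25; 6.25 / 76.5 = 8.2% higher; 1 − 1/1.082 = 7.6% lower.

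**4. Other assumptions.** A second grid of 108 covariance patterns (SDb 4 to 6; score SDs of 6 to 6.5 at Week 1 rising to 9.5 to 10 at Week 6; several baseline-to-visit correlations) gave reductions of 0.1% to 14.0%, median 1.4%. The 14.0% came from a pattern in which the correlation with baseline falls from 0.8 at Week 1 to 0.2 at Week 6. No figure here is a ceiling.

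**5. Effect on power.** Take 8.745 as the SD under the planned model and reduce its variance:

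- 2% lower: 91.0% and 76.2%; interval narrower by 1 − √0.98 = 1.0%.
- 5% lower: 91.9% and 77.8%; interval narrower by 1 − √0.95 = 2.5%.

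**The case against.** The best defence is that nothing here is wrong. Text and code agree, both forms of the model are conventional, and every input that drives the gain is assumed. If slopes barely change, the gain is essentially nil. That the slope steepens over time is itself an assumption; the documents neither support nor contradict it. The by-week ANCOVA will also show whether the restriction matters. All of this stands, and it keeps the point minor. It does not remove it: the ANCOVA is supportive, the multiplicity-adjusted p-values come from the MMRM, and the extra term costs next to nothing if it proves unnecessary.

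A reader might infer more than the documents support:

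- *That the primary contrast is biased or type I error inflated.* Under randomisation with complete data, neither follows. If dropout depends on baseline and slopes differ by visit, some bias is possible, but that was not quantified.
- *That the planned power is overstated.* It reproduces and claims no gain from visit-specific slopes.
- *That the plan contradicts itself*, because SAP 16.1.4.2 says: "Each sequential regression model (ie, for imputation of values at a given time point) will include explanatory variables for all previous" scores. Those regressions belong to a sensitivity analysis; the primary MMRM imputes nothing (SAP 16.1.2). They also condition on earlier visits, so their baseline coefficient is a partial effect and not the slope at issue. An imputation model richer than the analysis model is no defect.
- *That CGI-BP-S loses as much precision.* The calculation used MADRS-scale values only.

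**Conclusion.** The point holds as a minor, optional improvement. The primary MMRM constrains the baseline slope to be equal at Weeks 1, 2, 4 and 6, and relaxing this takes 3 parameters. Under the assumed SDs and correlation, the reduction in Week 6 variance is nil with equal slopes, typically about 0 to 3%, and about 5 to 8% only if slopes steepen from -0.10 to -0.65. Wider assumptions extend the range in both directions, with a median near 1.4%. All of this is for complete MADRS data. It is a matter of precision: the analysis as planned remains valid under randomisation with complete data, and the sample size stands.

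**What to change.** Before unblinding, add TOTBL*WEEK to the primary MMRM in SAP 16.1.3 and the Appendix 3 code, and record it in SAP 3.7 as a change from protocol 15.3.5.1. Appendix 6 already provides for documented changes ahead of unblinding. There is no treatment-by-baseline term, so the Week 6 treatment difference does not depend on the baseline value at which LS means are evaluated, and the LSMEANS statement can stay.

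For consistency, make the same change wherever the model is reused: CGI-BP-S, HAM-A and QIDS-SR16 (each with its own baseline), the MMRM steps applied to the imputed datasets in the placebo-based and tipping-point analyses, the MMRM feeding gMCP-Mod, and the subgroup MMRMs. The YMRS and movement-scale MMRMs also refer back to 16.1.3, so the SAP should say whether they follow.

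The cost is 3 parameters per model and edits in several places. If unblinding has already taken place, leave the primary model as written and report the extended model as supportive.

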15.3.5.1. Primary Efficacy Endpoint Analysis

The primary efficacy endpoint is the change from baseline in the MADRS total score at Week 6.

The primary efficacy estimand is defined as the efficacy of each SEP-4199 dose over placebo for 6 weeks, calculated as the difference in the primary efficacy endpoint between each SEP-4199 treatment group and the placebo treatment group in the ITT population. This estimand, which will only include those subjects who participate in sites located in US and Europe, provides an estimate of the efficacy of each SEP-4199 dose over placebo, should a subject be able to tolerate and adhere to treatment for 6 weeks.

The efficacy of SEP-4199 in terms of the MADRS total score will be evaluated using the following two null hypotheses:

H1: There is no difference in mean change from baseline at Week 6 on the MADRS total score in the SEP-4199 200 mg treatment arm compared to Placebo.

H2: There is no difference in mean change from baseline at Week 6 on the MADRS total score in the SEP-4199 400 mg treatment arm compared to Placebo.

The alternative hypothesis for each of the null hypotheses is that there is a difference, respectively. If at least, one of the primary comparisons demonstrate a significant result, the study will be considered positive.

The primary efficacy endpoint will be analyzed for the ITT population by means of an MMRM analysis, with change from baseline in the MADRS total score as the response variable and with factors for treatment group, visit, region, baseline MADRS total score, and the treatment-by-visit interaction. This analysis method makes a missing at random (MAR) assumption to the missing primary efficacy endpoints. The Kenward Roger approximation will be used to estimate denominator degrees of freedom. An unstructured covariance matrix will be used for the within-subject correlation. A robust sandwich estimator for the standard error of the fixed effects (Diggle 2002) along with a spatial exponential or a spatial power covariance structures will be assumed sequentially in case of a convergence problem. The first covariance structure to yield convergence will be used in the analysis.

The Least Square (LS) mean treatment differences (each SEP-4199 group minus placebo) of change from baseline at Week 6, their 2-sided 95% CIs, and the associated p-values will be calculated based on the MMRM.

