17.6.3. ABNORMAL INVOLUNTARY MOVEMENT SCALE (AIMS)

The AIMS is a clinician-rated assessment of abnormal movements consisting of unobtrusive observation of the subject at rest (with shoes removed) and several questions or instructions directed toward the subject. It contains seven items related to: facial, lip, jaw, and tongue movements, upper and lower extremity movements, and trunk movements. Three other items assess the subject at a global level, and two items assess dental status. The individual items on the AIMS are rated from 0 = ‘None’ to 4 = ‘Severe’. The (non-global) total AIMS score is the sum of items 1 through 7. The possible range for the total AIMS score is 0 to 28. Items 8 through 12 are not included in the total AIMS score. Higher values of the total AIMS score indicate increased severity in abnormal movement. If 1 or more of the AIMS total score items are missing at a visit, the score will be set to missing. Item 8, representing global severity score, will be summarized separately. AIMS is assessed at Visit 2/Baseline/Week 0, Visit 3/Week 1, Visit 4/Week 2, Visit 5/Week 4, and Visit 6/Week 6.

Document:

Author:

Version Number:

V2.0

Version Date:

21MAY2020

Template No: CS_TP_BS016 Revision 4
Effective Date: 01Apr2016

Reference: CS_WI_BS005

All summaries and analyses will be based on the SAF population. Descriptive statistics for absolute value and change from baseline will be displayed at each visit by treatment group. Each total score will be analyzed using MMRM and ANCOVA based on the change from baseline to Week 6 similar to the primary efficacy endpoint, with the respective baseline values as covariate (see [Sections 16.1.3](#) and [16.1.5.1](#)).

The AIMS total score at each visit will also be classified as 'abnormal' if either: at least two items have a response of 'mild' or higher; or at least one item has a response of 'moderate' or higher. Otherwise, non-missing total scores will be classified as 'normal'. This is a modification of the Schooler-Kane Criteria for Tardive Dyskinesia ([Schooler 1982](#)). Shifts from baseline will be summarized by visit, postbaseline overall (based on maximum severity), and treatment group.

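### The two sequential fallback covariance structures for the MMRM are the same equal-variance model, and using that model can bias the Week 6 contrast

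*SAP*

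**What the plan says.** The primary MMRM uses an unstructured within-subject covariance with Kenward-Roger degrees of freedom and treats missing scores as missing at random, without imputation (SAP 7.3 and 16.1.3). For non-convergence, SAP 16.1.3 provides a robust sandwich estimator "along with a spatial exponential or a spatial power covariance structures will be assumed sequentially in case the model fails to convergence". Appendix 3 repeats that "the spatial exponential or spatial power covariance structure will be assumed sequentially along with a robust sandwich estimator", and Protocol 15.3.5.1 has the same rule: "along with a spatial exponential or a spatial power covariance structures will be assumed sequentially in case of a convergence problem". In all three places the first structure to converge is used.

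The Appendix 3 code gives both structures WEEK (1, 2, 4, 6) as the only coordinate and the same subject variable, with no option that lets the variance differ by visit or group. Both REPEATED statements stand in one PROC MIXED call. That call omits the Kenward-Roger option and names no replacement.

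SAP 16.1.3 and Appendix 3 define the between-group effect size at each visit from the matching diagonal element of the fitted covariance matrix. Appendix 3 says this works under any structure.

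The rule reaches beyond MADRS. Other analyses refer back to the primary MMRM, for example AIMS in SAP 17.6.3: "Each total score will be analyzed using MMRM and ANCOVA based on the change from baseline to Week 6".

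**The concern.** A sequence of fallbacks should offer a different model at each step. Here the second step repeats the first, so if the data do not support the first, nothing different remains. There is also nothing between a fully free covariance and one that fixes a single variance for all visits and a correlation that decays only with time.

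This matters because the estimand analysis relies on MAR. With incomplete data, the likelihood estimate at Week 6 borrows from earlier visits through the fitted covariance, so a wrong covariance can shift the point estimate. The sandwich makes the standard error robust but leaves the estimate where it is.

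**Working it through.** **1. The plan's own figures.** SAP 3.4 gives "A total sample size of 279 evaluable subjects in US and Europe (93 per treatment group: SEP-4199 200 mg/day, SEP-4199 400 mg/day, and placebo" arms) and "This effect size corresponds to a treatment difference of -3.85 for a SEP-4199 dose with a common standard deviation of 8.745".
- Effect size: 3.85 / 8.745 = 0.440, as stated.
- Randomised per arm: 93 / 0.95 = 97.9, so 98, as stated.
- Power, from two z-tests sharing placebo (correlation 0.5), 1-sided alpha 0.025, 2,000,000 runs. Both are rejected if the larger p is at most (0.9 + 0.1/2) × 0.025; otherwise the smaller is rejected if at most 0.025/2. Result: 0.905 for at least one and 0.752 for both, against 0.9027 and 0.7517 in Appendix 4, Table 8. The statement of "about 75% power to reject both truly significant primary comparisons using the truncated Hochberg" procedure reproduces. This point does not touch the sample size.

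**2. The two fallbacks are one model.** For visits d weeks apart:
- SP(EXP): covariance = σ² exp(−d/θ)
- SP(POW): covariance = σ² ρ^d

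Set ρ = exp(−1/θ); then exp(−d/θ) = ρ^d for every d. Example: ρ = 0.9 gives θ = −1/ln 0.9 = 9.49. The lags among Weeks 1, 2, 4 and 6 are 1 to 5 weeks, and both forms give 0.900, 0.810, 0.729, 0.656 and 0.590. Numerically the matrices agree to 1e-16. In 30 large-sample REML fits the two structures gave the same deviance (difference at most 2e-9), the same ρ and the same Week 6 contrast.

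Covariance parameters: unstructured, 4 × 5 / 2 = 10; either fallback, 1 variance + 1 correlation = 2.

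**3. Bias of the Week 6 contrast if the fallback is used.** The documents give the Week 6 SD and the planned difference, but no SDs at other visits, no within-subject correlations, and no dropout rate or mechanism before Week 6. The 5% allowance ("An upward adjustment of approximately 5% is used to compensate for information lost due to subjects who are randomized" without any postbaseline primary data) does not describe dropout during treatment. Those inputs are therefore assumptions: six true covariances (equal or growing SD; exponential, compound-symmetric or intermediate correlation) and several monotone MAR dropout rules, with 400,000 subjects per arm in two arms, and no baseline or region terms. The true difference is −3.85; positive bias means a smaller apparent benefit.

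| Situation | Dropout | Bias |
|---|---|---|
| True covariance is equal-variance exponential | any rule run | 0 (within 0.01) |
| Dropout unrelated to outcome, or same dependence relative to the arm mean | – | 0 (within 0.01) |
| Same absolute-score rule in both arms, true effect present | 19-42% | +0.04 to +0.21 |
| Outcome-related in placebo only (poor response) | 25% / 19% | +0.33 to +0.72 |
| Opposite directions in the two arms | 25% / 25% | +0.67 to +1.47 |
| Opposite directions, heavier dropout | about 40% | +1.4 to +3.0 |

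The last three rows have a misspecified covariance. Reversing the dropout pattern reverses the sign. Fitting the true covariance gave a bias of at most about 0.01 throughout.

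**4. What the sandwich does.** 1,000 trials per setting, 93 per arm, fallback with sandwich SE, two-sided 0.05:
- Exponential truth, or the same dependence in both arms: 3.8-4.7% rejection under the null, power about 79% per comparison.
- Misspecified, placebo-only dependence: 5.6-6.3% and 63-67%.
- Misspecified, opposite dependence: 10-14% and 45-52%.

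The bias remains.

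**5. The effect-size SD.** Under the fallback every diagonal element equals σ². In a large-sample fit with complete data, an SD assumed to rise from 5 to 8.745 gives a common SD of about 7.16. The Week 6 effect size then reads 3.85 / 7.16 = 0.54 instead of 0.44. A rise from 6.5 gives about 0.5. With constant SD there is no material distortion. This needs no dropout.

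**The case against.** The strongest reply is that the rule will rarely be used where it matters. With four visits, 10 covariance parameters and about 290 subjects, the unstructured MADRS model should converge; that is a judgement, not a computed probability, and it stands. Failure is more plausible in the Japan-only model (about 45 subjects planned), in small subsets, or in mostly-zero scores such as AIMS. But Japan analyses are largely descriptive, and subgroup terms add fixed effects without adding covariance parameters.

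Other planned analyses would also help to expose a problem. Appendix 3 runs the tipping-point analysis from 0% penalty, which is a MAR estimate whose imputation does not use the spatial structure. Under assumed SDs of 5 to 8.745 and opposite dropout of about 23% per arm, the fallback gave −2.84 and the 0% imputation −3.84. (SAP 16.1.4.3 starts at 5%, so the 0% run rests on Appendix 3.) ANCOVA by visit uses no within-subject covariance, but it is only a partial check because it uses observed cases. These are sensitivity and supportive analyses; they do not repair the headline estimate.

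The two REPEATED lines are evidently alternatives, since the text above them says the structures are tried in sequence. That is a matter of tidying the code.

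A reader might infer that the fallback always biases the Week 6 contrast. The checks do not support that: two conditions must hold together, and without both the bias is zero or small.

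**Conclusion.** The identity is certain. On one time coordinate with positive correlation, the second fallback is the first one rewritten, and the only alternative to the unstructured model is an equal-variance structure with two parameters.

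The bias is conditional. It needs a true covariance that departs from equal-variance exponential and outcome-related dropout that differs between arms. Under the assumed inputs with about 20-25% dropout it was roughly 0.3 to 1.5 points, or 0.33 / 3.85 = 9% to 1.47 / 3.85 = 38% of the planned difference. It was at most about 0.2 when one rule governed both arms. The documents cannot fix where in that range the trial would lie, or the direction.

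A reader might also infer that the primary result or the planned power is in doubt. Neither follows: the power figures reproduce, and the primary model will probably never reach the fallback. The priority is minor.

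**What to change.** Before unblinding, replace the fallback list in SAP 16.1.3 and Appendix 3 with structures that differ and let the variance change by visit:
1. Unstructured, Kenward-Roger.
2. Heterogeneous Toeplitz (TOEPH), Kenward-Roger.
3. First-order ante-dependence (ANTE(1)), Kenward-Roger; it suits the unequal spacing.
4. One spatial structure with the sandwich estimator as the last step only, naming the degrees-of-freedom method.

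Steps 2 and 3 each have 4 variances + 3 correlations = 7 parameters. In a large-sample run with improvers leaving the active arm (16% / 24% missing, true −3.85), the spatial fallback gave −3.38, TOEPH −3.86 and ANTE(1) −3.84. In further runs the bias of TOEPH and ANTE(1) was about 0.2 or less. Do not use heterogeneous compound symmetry (CSH): it gave −4.06 there and −4.27 under opposite dropout, so it can exaggerate the effect.

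Put one REPEATED statement in each PROC MIXED call. If step 4 is reached, state that the effect-size SD is common to all visits.

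The cost is a few lines of SAP text and code. Nothing changes if the unstructured model converges.
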